8.0 PRETREATMENT EVALUATION

Due to the nature of disease, patients with PHC undergo extensive pre-operative work-up (e.g., laboratory testing, CT or MR imaging, biliary drainage, liver function tests) prior to surgical exploration and potential portal vein embolization. In the present study, patients that will undergo open RE during exploratory laparotomy will have undergone these preoperative work-up procedures as standard of care. Additionally, Quality of life will be assessed during the pre-treatment visit using the Functional Assessment of Cancer Therapy-Hepatobiliary instrument (FACT-Hep). FACT-Hep is a 45-item self-report instrument designed to measure QoL in patients with hepatobiliary cancers. It comprises the FACT-General (FACT-G) and the hepatobiliary subscale (Hep). The FACT-G consists of 27 items that measure 4 domains of well being in cancer patients: physical well being (PWB), social/family well being (SWB),

functional well-being (FWB), and emotional well-being (EWB). The instrument employs a Likert-type format (0 "not at all" to 4 "very much"). Lower total scores reflect lower QoL. The FACT-G score is a total of the subscale scores. The FACT-G has demonstrated internal consistency, score stability, reliability, and validity [34-39]. The Hep is a reliable and validated disease-specific subscale consisting of questions relating to pruritus, jaundice, and drainage catheters [40,41]. Patients will not be replaced if they do not complete these questionnaires.

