be determined by the distance between each pair of electrodes and will be aimed at 1500 V/cm, with the intent to generate at least 1000 V between electrodes. The electrodes will be placed in and around the tumor under ultrasound guidance according to the manufacturer's guidelines, aiming at a macroscopically complete ablation with a 5 mm margin, with the inter-electrode distances 10-24 mm and a maximum angulation between electrodes of 15°. The predicted treatment zone will be automatically calculated using the NanoKnife generator software according to a system-based protocol that takes into account the exact position of all electrodes. The number of probes used for ablation is dependent on tumor size. If the lesion is larger or has a different shape than the area that one set of probes can cover (according to manufacturer's guidelines), multiple ablations will be performed, until the whole tumor area is ablated. Number of probes, number of probe replacements (per probe) due to unsatisfactory placement, number of pulses (for each pair of electrodes), probe length, space between probes, pulse voltage (amplitude, Volt), pulse length (μsec), pulse interval (ms) will be carefully noted. All complications (cardiac and non-cardiac) will be carefully registered and monitored.

Specific attention will be paid to the placement of electrodes close to bile ducts as previous research demonstrated that biliary strictures may occur when needles are placed within 3 mm of the bile ducts [29, 42].

Post RE treatment

Patients will be monitored on the recovery and surgical wards daily, according to current medical practice. Patients with endoscopic or percutaneous plastic drains will be evaluated for definitive metal stents (fully-, partially- or uncovered self-expanding metal stents) or removal of drains if obstruction appears to be treated by RE in all patients through an endoscopic or percutaneous approach at least 7 days after the RE procedure. This 7-day window is built in to avoid manipulation of the biliary tree immediately after RE. Bile ducts to atrophic liver lobes will not be drained. Following exploratory laparotomy and open RE, patients will undergo treatment in an enhanced recovery program. Patients will be monitored on the recovery and the surgical ward daily and discharged when fully recovered from the laparotomy, according to current medical practice.

General treatment

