10.0 EVALUATION DURING TREATMENT/INTERVENTION

Data collection prior and during hospital admission

Prior to the procedure we will collect:

Baseline parameters: Demographics, tumor characteristics and serum markers that will be routinely collected are: age, sex, comorbidity, body mass index (BMI), tumor size, tumor growth pattern, arterial or venous vascular involvement, nodal status, cancer antigen (CA) 19.9, IgG4, albumin, C-reactive protein (CRP), leukocytes. If IgG4 level is normal at baseline further measurements are not necessary and will therefore not been included in the follow up.

During the hospital stay, we will collect data on serum liver enzymes and inflammatory parameters (WBC, CRP).

Follow up

During follow up, after discharge, patients will be seen in the outpatient clinic, as is routine practice for post-operative/post-procedural patients, for clinical evaluation and laboratory testing of liver enzymes, inflammatory parameters (WBC, CRP), Albumin and tumor markers (CA 19.9).

In this study, patients will also be seen in the outpatient clinic at 2 weeks, 4 weeks, and approximately 6, 12, and 24 months, as is routinely performed for clinical follow-up currently. Laboratory tests obtained at visits after the first post-procedure visit will be determined by the surgeon.

The date of disease progression is defined as the date of CT scan on which the first suspected lesion is defined.

Quality of life will be assessed at the initial clinic visit, initial post-operative visit (2 weeks from surgery), and at subsequent post-operative visits \pm 1 month from 3, 6, 9, 12, and 24 months following the IRE procedure. The Functional Assessment of Cancer Therapy-Hepatobiliary instrument (FACT-Hep) will be used. If patients are unable to complete the questionnaires at the designated visits for any reason, they will be offered the option of returning the QOL via mail.

Imaging

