14.1 BIOSTATISTICS

The primary objective of this study is to assess biliary drainage patency after IRE treatment of hilar cholangiocarcinoma. In patients with plastic percutaneous drains this is defined as ability to remove plastic biliary drains within 15 months of the IRE procedure without need for reinsertion of a drain or stent. For patients with metal stents in place the definition of patent biliary drainage is 4-months without cholangitis post IRE procedure.

We will enroll 20 patients. Mean patency is approximately 1.5 months for plastic stents and 4 months for metal stents. Assuming an exponential distribution time to failure, we extrapolate that the patency rate at 15 months for plastic stents and at 4 months for metal stents will approximately be 37% and we will use this number as our historical control rate. If 10 or more of the 20 patients we plan to enroll display patency (at 1.5 months for plastic and 4 months for metal stents) then we will recommend IRE for further study. This decision rule has 8% Type I error and 12% Type II error for distinguishing between patency rates of 37% and 65%.

The secondary outcomes of interest are:

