- Safety will be assessed by determining the proportion of patients experiencing a clinically relevant complication within 30 days post-IRE, defined as CTCAE (version 5.0) grade 3 or higher complications requiring re-intervention, prolonged hospital stay, intensive care admission, re-admission or leading to mortality. After accruing the first 8 patients, we will do an interim analysis of safety. If 4 or more of these 8 patients experience a grade 3 complication within 30 days post-IRE (as defined above) then the study will stop for lack of safety. A 30 day observation window will follow after the eighth patient is enrolled. If one patient in the first 8 patients has a grade 4 or 5 complication the study will be halted. If none of these conditions are met then we will accrue another 12 patients. If 6 or fewer of the total group of 20 patients have a grade 3 complication we will conclude that the safety endpoint has been met. This safety monitoring rule has an 81% chance of stopping the study early for safety concerns if the true probability of complications is 35%. If there is a death during the 30-day post-procedure period the study will be halted to examine the relationship of death to the procedure. We will examine the cause of death for all 30-day deaths and determine if it could be related to the procedure. If the death can possibly be related to the

procedure then the protocol will be stopped. To continue with the protocol after a death, we will submit to RB all the documentation related to the ascertainment of cause of death and describe how it cannot be related to the RE procedure.

- Duration of hospital stay will be summarized with median, range and quartiles.
- Quality of life will be summarized by average subscale scores at each visit and change from previous visit will also be reported by the same summary statistics.
- Tumor response on CT imaging and blood biomarker response will be reported as a binomial proportion with a 95% confidence interval. RECIST criteria cannot be applied to Klatskin tumors as they are radiographically difficult to assess. This instead will be a subjective evaluation of the ablation zone to determine the appearance of an RE associated ablation zone in the hilar area. This is currently unknown.
- Time between RE and start of palliative chemotherapy will be summarized with median, range and quartiles
- Duration of palliative chemotherapy will be summarized using Kaplan-Meier statistics

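### Quality of life is summarized by visit averages and change from the previous visit, with no paired change from the pre-IRE score that the trial collects

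*Combined protocol and SAP*

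**What the plan says.** Section 14.1 gives two summaries for this outcome. The first is a level: "Quality of life will be summarized by average subscale scores at each visit". The second is a change: "change from previous visit will also be reported by the same summary statistics". No other quality-of-life contrast is defined. The section gives no test or success criterion for this outcome, and no handling of deaths or missing forms.

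FACT-Hep is completed before treatment (sections 8.0 and 10.0), at the 2-week postoperative visit, and then around "3, 6, 9, 12, and 24 months following the IRE procedure" (section 10.0). On direction, section 8.0 states: "Lower total scores reflect lower QoL".

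IRE is done through a laparotomy (section 6.1). Section 9.0 describes the aftercare: "Following exploratory laparotomy and open RE, patients will undergo treatment in an enhanced recovery program". The same section holds off evaluation of plastic drains for removal or metal stenting until at least 7 days after IRE.

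**The concern.** Quality of life is a listed secondary objective (section 2.1), and section 3.0 names its improvement as a goal of palliative drainage. In a single-arm study the natural question is whether patients are better or worse than before IRE. The pre-IRE score enters only one planned change, the one to 2 weeks.

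The next change, at 3 months, uses the 2-week score as its reference. That score falls in surgical recovery. Some drains may still be in place, and section 8.0 says the hepatobiliary subscale asks about drainage catheters. A depressed reference gives a positive 3-month change even if patients have not regained their starting level. The plan uses the pre-treatment reference elsewhere: section 12.0 defines biomarker response against the pre-treatment value.

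What is at stake is the reading of one descriptive outcome. A report that stressed the change figures could present surgical recovery as a gain from IRE.

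**Working it through.** The plan states no effect size, standard deviation or completion rate for quality of life, so there is no figure to reproduce. Three checks follow. All scores and completion rates in them are assumptions.

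**1. Two reference points on one score path.** Assumed mean scores, in arbitrary units where higher is better, in patients who all complete every form:

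| | Pre-IRE | 2 wk | 3 mo | 6 mo | 9 mo | 12 mo | 24 mo |
|---|---|---|---|---|---|---|---|
| Mean score | 60 | 45 | 50 | 53 | 54 | 55 | 55 |
| Change from previous visit | – | −15 | +5 | +3 | +1 | +1 | 0 |
| Change from pre-IRE | – | −15 | −10 | −7 | −6 | −5 | −5 |

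Every planned change after week 2 is zero or positive, yet patients stay below their starting level throughout. With complete data the planned output still reveals this: the averages run from 60 to 55, and the planned changes sum to −15 + 5 + 3 + 1 + 1 + 0 = −5.

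**2. How far the group shrinks.** Section 3.0 cites survival of 14 to 16 months for locally advanced disease. Reading this as a median M and assuming exponential survival, the proportion dead by month t is 1 − 0.5^(t/M). For M = 15:

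- 3 months: 1 − 0.5^(3/15) = 13%
- 6 months: 1 − 0.5^(6/15) = 24%
- 12 months: 1 − 0.5^(12/15) = 43%
- 24 months: 1 − 0.5^(24/15) = 67%

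For M from 16 down to 14 the ranges are 12–14%, 23–26%, 41–45% and 65–70%. Section 14.1 states: "We will enroll 20 patients". At M = 15 about 20 × 0.33 = 6.6 of them would be alive at 24 months, before any missing forms.

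**3. What attrition does to the visit averages.** The path above was simulated 4,000 times with 20 patients, a between-patient SD of 12 and a within-patient SD of 6. Assumed completion across the seven visits was 100, 95, 85, 70, 60, 50 and 25%. Dropout was either unrelated to a patient's underlying score level or more likely at low levels (moderate or strong dependence).

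| Dropout | Average at 3 mo | at 9 mo | at 12 mo | at 24 mo | Paired change from pre-IRE at 24 mo |
|---|---|---|---|---|---|
| Unrelated | 50.0 | 54.0 | 55.1 | 55.1 | −5.0 |
| Moderate | 52.2 | 59.3 | 61.5 | 65.3 | −5.0 |
| Strong | 52.8 | 60.7 | 63.3 | 68.1 | −5.0 |

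The pre-IRE average is 60.0 in every row. At 3 months the averages still show the loss. By 9 to 12 months under selective dropout they have reached or passed 60, although each patient's expected change is still a loss.

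One limit matters. The simulation gives every patient the same mean path, so pairing recovers −5 by construction, and the successive changes also still sum to −5. With real patients whose courses differ, each successive change is averaged over a different group, and the sum need not be the net change of any one group. If patients who are deteriorating are the ones lost, paired change is selective too.

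**The case against.** The tempting stronger reading is that the plan reports quality of life only as visit-to-visit change, so that recovery from surgery will appear as improvement and a net loss will be hidden. The documents do not support that.

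- The same sentence in section 14.1 plans the visit averages first and the change in addition. A baseline average will sit beside every later one.
- The first reported change runs from pre-IRE to 2 weeks. There the previous visit is the baseline, so any postoperative fall is shown in full. The favourable-looking figure is the second change, and it misleads only if read alone.
- The documents neither state nor quantify a 2-week low. It is plausible after laparotomy, no more.
- The two mechanisms act at different times. The rebound matters at 3 months, when about 13% would have died and the averages still come largely from the same patients, apart from non-response. Attrition matters later, when the reference is no longer the 2-week visit.
- Pairing does not solve death or non-response. It compares the same patients with themselves but says nothing about those who are gone.
- Forms may be returned by mail (section 10.0), and routine reports assess missing data (section 16.2).

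All of this stands, and it limits the point to what can be misread. It does not remove it: no planned figure is a within-patient contrast with the pre-IRE score after week 2, and the averages become a poor substitute as the group shrinks.

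**Conclusion.** The omission is real, and its effect is moderate. The 3-month change can look like improvement while patients remain below their pre-IRE level. The averages offset this well early and less well later, because by 12 and 24 months about 43% and 67% of patients would have died. Those percentages rest on reading the cited survival as a median of about 15 months with exponential survival. The direction of any distortion in the later averages depends on whether patients with low scores are lost sooner, which the documents do not address.

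A reader might also infer that the trial's conclusion is at risk. It is not: the recommendation for further study rests on patency in at least 10 of 20 patients, and quality of life plays no part in it.

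**What to change.** In section 14.1, add for each FACT-Hep subscale and each post-IRE visit the paired change from the pre-treatment score in patients with both values, preferably with a 95% confidence interval. Beside it, give the number assessed out of the number alive. Keep the visit averages, and keep visit-to-visit change as a supplement. State that the paired change describes surviving responders only.

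The cost is a few lines in the analysis section. The pre-treatment score is already collected, so no visit, form or patient is added. Fixing the reference point now also prevents it from being chosen after the scores are seen.

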The primary outcome is patency of biliary drainage. In patients with plastic percutaneous drains this is defined as ability to remove plastic biliary drains within 1.5 months of the IRE procedure without need for reinsertion of a drain or stent. For patients with metal stents in place the definition of patent biliary drainage is 4-months without cholangitis post IRE procedure.

Secondary outcomes are the success rate of completing IRE (defined as percentage of planned pulses completed}, complications, duration of hospital stay, quality of life, impact of IRE on post-procedural CT imaging and blood biomarker response, time between IRE and start of palliative chemotherapy, metal stent patency, progression-free and overall survival. Prolonged hospital stay is defined as hospital stay for more than 10 days. The average length of stay for major liver procedures is 8 days. Patients with hilar cholangiocarcinomas often have biliary drains and stents so require extra care as inpatients after any procedure. Complications will be defined as patients experiencing a clinically relevant IRE-related complication within 30 days post-IRE, defined as CTCAE (version 5.0} grade

3 or higher complications requiring re-intervention, prolonged hospital stay, intensive care admission, re-admission or leading to mortality.

Follow up: 30 days after intervention for the primary endpoint. For survival endpoints, there is a 2-year followup.

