2.1 OBJECTIVES AND SCIENTIFIC AIMS

Primary objective:

The primary objective of this study is to assess patency of biliary drainage. In patients with plastic percutaneous drains this is defined as ability to remove plastic biliary drains within 1.5 months of the IRE procedure without need for reinsertion of a drain or stent. For patients with metal stents in place the definition of patent biliary drainage is 4-months without cholangitis post IRE procedure.

Secondary objective:

The secondary outcomes of interest are

- Duration of hospital stay
- Complications
- Quality of life
- Tumor response on CT imaging and blood biomarker response
- Time between IRE and start of palliative chemotherapy
- Duration of palliative chemotherapy
- Progression-free and overall survival
- Success rate of completing IRE (defined as percentage of planned pulses completed)

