CT and rvRI scans used for routine clinical care will be used for this protocol. If patients are receiving chemotherapy, a pre-chemotherapy scan will be obtained 4-6 weeks post procedure, as per standard clinical practice. If no chemotherapy is planned a scan at 4-6 weeks will be clinically appropriate to assess disease progression, treatment response, and stent patency. Scans every 4-6 months will be used in patients on and off chemotherapy to evaluate for disease progression, which is consistent with current practices for routine management of patients with PHC. Tumor response is defined as a loss of enhancement for hypervascular tumors and as a lack of persistent tumor rim enhancement for hypovascular tumors on contrast imaging studies. Persistent disease is defined as residual tumor enhancement on the posttreatment imaging studies, and local recurrence is defined as an enhancing tumor within 1cm of an ablation zone.

In order to diagnose complications such as biliary leakage, intra-abdominal abscesses or bleeding, ultrasound and CT are used. When disease progression is expected, a CT is performed to confirm (or refute) the clinical suspicion. This procedure is consistent with normal clinical standards.

Follow up of subjects withdrawn from treatment

Patients withdrawn from treatment will not have undergone the RE procedure and are therefore considered not to have participated in this study. These subjects will receive normal follow-up outside this study.

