12.0 CRITERIA FOR THERAPEUTIC RESPONSE/OUTCOME ASSESSMENT

The primary endpoint is biliary drainage patency. This will be measured as a marker of therapeutic response. Biliary drainage patency in patients with metal stents is defined as the period between RE treatment and stent occlusion or patient death. Occlusion of the stent is a clinical event. This is defined as recurrent jaundice with cholestasis, cholangitis (fever, increase in serum bilirubin, leukocytosis), stent failure that leads to replacement of a stent, or need to insert a new drain or stent within 4 months. Biliary drainage patency failure in patients that with plastic drains is defined as patients that cannot have plastic drain removed within 1.5 months of the RE.

The patients and caregivers are told about the symptoms of cholangitis and are asked to contact our hospital immediately in case of signs of obstruction. If stent obstruction is suspected, ERC will be performed and stents are changed if necessary.

Tumor response will not be evaluated in this trial by imaging via RECIST criteria as Klatskin tumors are difficult to measure as they are growing along the biliary tract.

Subjective evaluation of the ablation zone to determine the appearance of an RE associated ablation zone in the hilar area will be performed on postoperative scans.

Persistent disease is defined as residual tumor enhancement on the first post-treatment imaging study, and local recurrence is defined as an enhancing tumor within 1 cm of an ablation zone.

As a secondary endpoint we are measuring overall survival. If there is a response to our treatment, we would expect there may be a longer overall survival.

Response on blood biomarker is defined as decrease of blood marker by >20% from the pre-treatment value.

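### The progression date is defined by CT alone although MRI is an accepted follow-up scan, so progression first seen on MRI is dated late and PFS can only lengthen; the response endpoint's CT label needs the same correction

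*Combined protocol and SAP*

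**What the plan says.** **Imaging used.** Section 10.0 (Imaging) states: "CT and rvRI scans used for routine clinical care will be used for this protocol". The garbled word is MRI, misread from the PDF. The 4-6 week post-procedure scan and the surveillance scans every 4-6 months are described without a modality. Section 8.0 accepts CT or MR at work-up, and section 9.0 (General treatment) expects IRE effects to be read on either.

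**Progression date.** Section 10.0 (Follow up) states: "The date of disease progression is defined as the date of CT scan on which the first suspected lesion is defined". No other section defines a progression date. The Imaging part of section 10.0 adds that a CT is done to confirm or refute suspected progression. It gives no time window.

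**Response endpoint.** CT is named in three places: section 1.0 ("impact of IRE on post-procedural CT imaging and blood biomarker response"), section 2.1 ("Tumor response on CT imaging and blood biomarker response") and section 14.1 ("Tumor response on CT imaging and blood biomarker response will be reported as a binomial proportion with a 95% confidence interval"). The operational definitions are wider. In section 10.0, response for hypovascular tumors is a "lack of persistent tumor rim enhancement for hypovascular tumors on contrast imaging studies". In section 12.0, "Persistent disease is defined as residual tumor enhancement on the first post-treatment imaging study", and the ablation-zone reading for the "hilar area will be performed on postoperative scans".

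**Analysis.** Section 14.1 summarizes PFS by Kaplan-Meier methods and reports response as a proportion with a confidence interval. No test or comparator is attached to either.

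**The concern.** A PFS event should carry the date of the scan that first showed progression. Here the rule recognizes one modality while the follow-up uses two. A patient followed by MRI can show a new lesion on a routine scan and still have no event under the definition until a CT shows it. The error runs one way: a later CT can move the event date back in time for nobody, and forward for some. PFS is a stated secondary outcome, and in a single-arm study readers will set it beside published figures, so a one-sided dating rule should not be left in.

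The response endpoint has a lesser problem. Its label says CT and its definition does not, so two analysts could treat an MRI reading differently.

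**Working it through.** The plan gives no figure that depends on modality, so there is nothing to reproduce. The check is a reading of the text followed by an illustration of size.

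**Step 1: follow a patient whose progression is first seen on MRI.**

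| Situation after the MRI | Progression date under section 10.0 | Effect on PFS |
|---|---|---|
| Confirmatory CT done and shows the lesion | Date of that CT | Later by the MRI-to-CT gap |
| CT done, lesion not visible on it | None until a later CT shows it | Later, or no progression event |
| CT not done | None | No progression event |

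In no row is the date earlier than the MRI. The confirmatory CT limits the delay but does not remove it, because the CT date still replaces the MRI date.

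**Step 2: inputs for the size.**
- Median PFS m = 8 months: the background figure for gemcitabine plus cisplatin in section 3.0, used only as a plausible scale.
- Share p of progressions first seen on MRI: not in the documents; assumed 10%, 25% and 50%.
- MRI-to-CT gap d: not in the documents; assumed 0.5 and 1 month for a prompt confirmatory CT.
- Exponential event times, every event a progression. Deaths without progression would not be shifted, so this assumption leans towards a larger effect.

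**Step 3: formula.** With λ = ln 2 / 8 = 0.0866 per month, the reported survival curve for t > d is

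S(t) = exp(-λt) × [1 - p + p × exp(λd)].

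Setting S(t) = 0.5 gives

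reported median = 8 + ln[1 + p × (exp(λd) - 1)] / λ.

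**Step 4: results.** exp(λd) = 1.0443 for d = 0.5 and 1.0905 for d = 1.

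| p | d = 0.5 month | d = 1 month |
|---|---|---|
| 10% | 8.05 | 8.10 |
| 25% | 8.13 | 8.26 |
| 50% | 8.25 | 8.51 |

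Worked case, p = 50% and d = 1: 8 + ln(1 + 0.5 × 0.0905) / 0.0866 = 8 + 0.51 = 8.51 months. A simulation of 400,000 event times gave 8.03 to 8.49 over the same grid, which agrees within simulation error.

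**Step 5: response label against definition.** Sections 1.0, 2.1 and 14.1 say CT. Section 10.0 says contrast imaging studies, and section 12.0 refers to the first post-treatment imaging study and to postoperative scans. The definitions do not restrict modality. Section 14.1 states no denominator and does not exclude a patient imaged only by MRI.

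**The case against.** The best defence is that this is editorial. Suspected progression triggers a CT, so the date will usually be close to right. Both endpoints are secondary and descriptive in 20 patients: at an observed response of 50%, the exact 95% interval is already 27.2% to 72.8%. Nothing in the primary analysis turns on the modality.

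Most of that stands, and it sets the size of the point. It does not remove the point. The confirmatory CT has no time window, and under the rule its date is the one recorded even when an MRI showed the lesion first.

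A reader might infer three stronger things, which the documents do not support:

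- *Progression seen on MRI is missed.* Section 10.0 plans a CT when progression is suspected. An undefined date arises only if that CT is not done or does not show the lesion.
- *Patients followed by MRI drop out of the response proportion.* No section excludes them, and the definitions in sections 10.0 and 12.0 admit any contrast or post-treatment imaging. Nor do the documents link the choice of modality to prognosis, so a selected subset is not shown.
- *PFS is inflated by months because the event waits for the next routine scan.* With d = 4 to 6 months, the formula gives a median of about 9.1 to 9.8 months at p = 25%. That sets aside the confirmatory CT. It also treats the 4-6 month interval as a CT interval, when the plan names no modality for those scans.

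**Conclusion.** The point holds for the progression date. Section 10.0 contains the only definition, it names CT alone, and the same section uses MRI. The direction is certain: PFS can only be lengthened relative to dating by the first scan that shows the lesion. The size is probably small. With a prompt confirmatory CT, a true median of 8 months would be reported as about 8.0-8.5 months. That range rests on an assumed MRI share of 10-50%, an assumed gap of 0.5-1 month and exponential event times. The documents give neither the share nor the gap.

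For the response endpoint, the fault is a label narrower than the definition behind it. The documents do not establish a loss of patients or a bias in the proportion.

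This is a minor point. The primary patency rule, the sample size of 20 and the error rates do not depend on it.

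**What to change.** 1. In section 10.0 (Follow up), define the progression date as the date of the first CT or MRI that shows the lesion. If a later CT confirms what an MRI showed, the MRI date stands.
2. In sections 1.0, 2.1 and 14.1, replace the reference to CT imaging in the response endpoint with contrast-enhanced CT or MRI, to match the definition in section 10.0.
3. In section 14.1, it would help to add one sentence giving the denominator of the response proportion and how a patient without an assessable scan is counted, since neither is stated.

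The cost is wording only. The scans are already obtained in routine care, so no visit or image is added.
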